**Table 1: Primary Safety Endpoint Definitions**

Term	Definition
Transient Ischemic Attack (TIA)	New focal neurological deficit with rapid symptom resolution (usually 1 to 2 hours), always within 24 hours; neuroimaging without tissue injury. 
Vagal Nerve Injury/Gastroparesis	Vagal nerve injury is defined as injury to the vagal nerve that results in esophageal dysmotility or gastroparesis. Vagal nerve injury is considered to be a major complication if it prolongs hospitalization, requires hospitalization, or results in ongoing symptoms for more than 30 days following an ablation procedure. 
Vascular access complications	Development of a hematoma, an AV fistula, or a pseudoaneurysm. A major vascular complication is defined as one that requires intervention, such as surgical repair or transfusion, prolongs the hospital stay, or requires hospital admission. 

#### **4.2. Primary Effectiveness Endpoint**

The primary effectiveness endpoint is defined as the event-free rate at 12 months post-procedure.

Primary effectiveness events are defined as:

- Acute procedural failure
- More than one repeat procedure during the blanking period (90 days post index procedure)
- Documented atrial fibrillation, or new onset of atrial flutter or atrial tachycardia event ( $\geq$  30 seconds in duration from an event monitor or Holter, or from a 10 second 12-lead EKG) between 91 days and 365 days post index procedure
- Any of the following interventions for atrial fibrillation, or new onset of atrial flutter or atrial tachycardia between 91 days and 365 days post index procedure:
  - Repeat procedure
  - Cardioversion
  - Prescribed any AAD\*

\*AADs for endpoint will consist of all Class I/III and any Class II/IV medications taken for control of AF/AT/AFL recurrence

#### **4.3. Secondary Effectiveness Endpoint**

Secondary effectiveness endpoint is defined as the event-free at 12 months post-procedure.

Secondary effectiveness events are defined as:

- Acute procedural failure
- More than one repeat procedure during the blanking period (90 days post index procedure)
- Documented symptomatic atrial fibrillation, or new onset of atrial flutter or atrial tachycardia event ( $\geq$  30 seconds in duration from an event monitor or

Holter, or from a 10 second 12-lead EKG) between 91 days and 365 days post index procedure

- Any of the following interventions for atrial fibrillation, or new onset of atrial flutter or atrial tachycardia between 91 days and 365 days post index procedure:
  - Repeat procedure
  - Cardioversion
  - Prescribed a higher dose of any AAD\* documented at baseline
  - Prescribed a new AAD\* not documented at baseline

\*AADs for endpoint will consist of all Class I/III and any Class II/IV medications taken for control of AF/AT/AFL recurrence

#### **4.4. *Tertiary Endpoints***

**Chronic Effectiveness:** Evaluation of chronic recurrence at 24 months and 36 months

- Recurrence is defined as intervention for atrial fibrillation, or new onset of atrial flutter or atrial tachycardia (repeat procedures, use of AADs, cardioversion), excluding repeat procedures during the 90-day blanking period.
- Data collection to include the diagnostic modality used to identify recurrence and the therapeutic intervention
- Chronic effectiveness will be evaluated using Kaplan-Meier methodology. The Kaplan-Meier 24 month and 36 month chronic recurrence-free rate will be calculated and presented along with the 95% confidence interval, calculated as the pointwise confidence limit using the log-log methodology. Subjects who withdraw from the study prior to the specified time point without experiencing an event will be censored on the date of withdrawal.

**Center Experience:** Primary Safety and Primary Effectiveness outcomes by center experience

- In order to evaluate training effectiveness for investigators outside of the ZERO AF IDE study, outcomes in centers performing five or more procedures using the Blazer OI catheter during the ZERO AF IDE study will be compared to all other. Kaplan-Meier rates and 95% confidence intervals for the Primary Safety and Effectiveness endpoints for both groups will be presented with no statistical comparison.

**Safety:** Reportable Adverse Events rates at 12, 24 and 36 months

Adverse events will be collected at all subject follow-up visits.

Reportable events include:

- All Serious Adverse Events
- All Study Procedure-Related Adverse Events
- All Study Device-Related Adverse Events
- All Study Device Deficiencies
- Unanticipated Adverse Device Effects/Unanticipated Serious Adverse Device Effects previously not defined in the Directions For Use.

Adverse event rates will be calculated using binomial methodology. The cumulative number of events and event rate will be included in all study reports. Subjects at risk for an adverse event will be determined by the subject treatment status; all treatment and attempt subjects will be considered at risk for study related adverse events

**Effectiveness: Acute Procedural Success Rate**

Acute Procedural Success is defined as pulmonary vein isolation achieved with a Boston Scientific OI ablation catheter as demonstrated by map-based entrance block with exit block and other maneuvers (such as adenosine testing) at the discretion of the physician.

## 5. Study Design

The INTERRUPT AF study is a global, prospective, non-randomized, multicenter study. The study will serve as the Post Approval Study for the Blazer OI, IntellaNav OI, IntellaTip MiFi OI, and IntellaNav MiFi OI Ablation catheters. All study devices will be used per instruction as they become commercially available after regulatory approval in their geography. Therefore, the index procedure for the INTERRUPT AF study is the same procedure that a subject would undergo if they were not participating in this study.

For the purposes of the study, De Novo is defined as subjects undergoing first ablation procedure for PAF with no prior left atrium ablations (RF, Cryo, Surgical).

### 5.1. *Scale and Duration*

A total of 415 subjects will be included in the study to ensure a minimum of 329 TREATMENT subjects.

The study is global and will include 25-50 sites in the United States, Europe and Asia-Pacific. A minimum of 50% of the sites will be selected from the United States.

To reduce the impact of individual center bias, no study site will be allowed to contribute more than 41 subjects (10% of the 415 enrollments requirement).

Each subject will be followed at specified time points after the ablation procedure (index procedure) with a follow-up duration of three years. A study subject's participation will be considered complete when all protocol required visits have been completed as indicated in Figure 5.2-1.

Accordingly, the study is expected to be completed in approximately five years (two-year enrollment period with three-year follow-up).

[figure not shown]

Figure 5.1-1: INTERRUPT AF Study Design

Table 2: INTERRUPT AF Study Timeline

Milestone	Forecast Date
Start	Upon FDA approval of PAS Protocol
First Enrollment	Approximately 120 days after FDA approval of the protocol
Enrollment Plan	Given the global prevalence of Paroxysmal Atrial Fibrillation, it is estimated that each activated site can each enroll 1 subject per month. It is anticipated that it will take 12-24 months to enroll the 415 subjects.
Progress Updates	Progress reports will be provided every six months for the first two years from the date of FDA Approval of PAS Protocol , then annually thereafter. Section 9.3.1 contains details of the progress report content.
Primary Objective Analysis	Within 3 months of 12-Month Visit Completion for all subjects.
Final Post Approval Study Report	Within 3 months of 36-Month Visit Completion for all subjects.

Anticipated Reporting Dates	Assuming FDA Approval of PAS Protocol on 01NOV2018, First Patient In on 01APR2019 and 18-month enrollment period: 

• 6 Month Interim PAS Status Report (~01MAY2019)

• 12 Month Interim PAS Status Report (~01NOV2019)

• 18 Month Interim PAS Status Report (~01MAY2020)

• 24 Month Interim PAS Status Report (~01NOV2020)

• 36 Month Interim PAS Status Report (~01NOV2021)

• 48 Month Interim PAS Status Report (~01NOV2022)

 

• Primary Objective Analysis (~01DEC2021)*

• Final Post Approval Study Report (~01DEC2023)

 
* The Primary Objective Analysis will be provided within 3 months of all 12 Month visits being completed in a Primary Endpoint Report. If the timing of the Primary Endpoint Report aligns with a scheduled interim report, the two will be combined.

------------------------------------	---

## **5.2. Treatment Assignment**

All subjects who meet the eligibility criteria as per Sections 6.2 and 6.3 and sign the informed consent will be considered enrolled. Subjects will be classified based on patient status classification as per Section 7.3.

## **5.3. Justification for the Study Design**

This post-market study aims to collect acute and long-term data for the Rhythmia Mapping System and Boston Scientific OI Catheters for de novo PAF ablation.

The Blazer OI, IntellaNav OI, IntellaTip MiFi OI, and IntellaNav MiFi OI Ablation Catheters have been approved by FDA for ablation treatment of PAF. The present study serves to comply with the request of providing continued reasonable assurance of the safety and effectiveness of the approved devices in a de novo PAF population. Any of the BSC Open Irrigated study catheters listed in Section 3.1 are allowed for use in the study once they are commercially available after regulatory approval in their geography for PAF Ablation.

# **6. Subject Selection**

## **6.1. Study Population and Eligibility**

Subjects included in the INTERRUPT AF study should be selected from the investigator's general patient population indicated for catheter ablation of PAF. Investigators are responsible for screening all potential subjects and selecting those who meet the eligibility criteria for the study as described in Sections 6.2 and 6.3 below.

### **6.2. Inclusion Criteria**

Subjects who meet all of the following criteria (see Table 3) may be given consideration for inclusion in this clinical investigation, provided no exclusion criterion (see Section 6.3) is met.

**Table 3: Inclusion Criteria**

Inclusion Criteria	

1. History of recurrent symptomatic Paroxysmal Atrial Fibrillation, defined as AFib that terminates spontaneously or with intervention within seven days of onset. Minimum documentation includes a physician's note indicating recurrent self-terminating Atrial Fibrillation AND one electrocardiographically documented AF episode within 6 months prior to enrollment.

2. Subjects who are eligible for an ablation procedure for Paroxysmal Atrial Fibrillation with the Rhythmia Mapping system according to current international and local guidelines;

3. Subjects who are eligible for an ablation procedure for Paroxysmal Atrial Fibrillation with a BSC Open-Irrigated Ablation Catheter according to current international and local guidelines;

4. Subjects who are willing and capable of providing informed consent;

5. Subjects who are willing and capable of participating in all testing associated with this clinical investigation at an approved clinical investigational center;

6. Subjects whose age is 20 years or above, or who are of legal age to give informed consent specific to state and national law.

--------------------	---

### **6.3. Exclusion Criteria**

Subjects who meet any one of the following criteria (Table 4) will be excluded from this clinical study.

**Table 4: Exclusion Criteria**

Exclusion Criteria	
 
1. Subjects enrolled in any other concurrent clinical study, with the exception of local mandatory governmental registries and observational studies/registries, without the written approval from Boston Scientific
 
2. Subjects unable or unwilling to complete follow-up visits and examination for the duration of the study;
 
3. Subjects who have undergone any previous left atrial cardiac ablation (RF, Cryo, surgical)
 
4. Subjects who have undergone any cardiac ablation within 30 days prior to enrollment;
 
5. Unrecovered/unresolved Adverse Events from any previous invasive procedure;
 
6. Life expectancy <= three years per physician opinion
 
7. Women of childbearing potential who are, or plan to become, pregnant during the time of the study (method of assessment upon physician's discretion)
 
8. Known cardiac thrombus within 60 days prior to enrollment
 
9. History of CVA, TIA or PE within 90 days prior to enrollment
 
10. Implanted pacemaker, ICD, or CRT leads within 90 days prior to enrollment
 
11. Implanted Left atrial appendage closure device prior to index procedure
 
12. Prosthetic mitral or tricuspid heart valves (subjects with successful mitral valve repair allowed- annular ring constitutes repair)
 
13. Left atrial diameter greater than 5.5cm
 
14. Documented or suspected stenosis of any pulmonary veins.
 
15. Atrial fibrillation secondary to electrolyte imbalance, thyroid disease, or reversible or non-cardiac cause.
 
16. Contraindication for anticoagulation
 
17. Clinically significant mitral valve regurgitation or stenosis per investigator discretion.
 
18. Any cardiac surgery <math>\leq</math> 90 days from consent date.
 
19. Any electrocardiographically documented episode of Persistent AFib, defined as AFib lasting longer than 7 days from onset.
 

--------------------	--

## 7. Subject Accountability

### 7.1. *Point of Enrollment*

Investigators will select subjects who are appropriate for study inclusion as per eligibility criteria (Section 6.2 and 6.3). Subjects who meet all eligibility criteria and have signed and dated the Informed Consent Form are considered enrolled in the study. All subject enrollments will be counted against the enrollment ceiling for the study.

### ***7.2. Withdrawal***

All subjects enrolled in the clinical study (including those withdrawn from the clinical study) shall be accounted for and documented. If a subject withdraws from the INTERRUPT AF study, the reason(s) shall be reported.

Reasons for withdrawal may include physician discretion, change in inclusion/exclusion status, subject choice to withdraw consent, lost to follow-up, or death. While study withdrawal is discouraged, subjects may withdraw from the study at any time, with or without reason, and without prejudice to further treatment. All applicable electronic case report forms (eCRFs) up to the point of subject withdrawal and an “End of Study” eCRF must be completed. For subjects who are “lost to follow-up” the investigator/center should have at least three documented attempts to contact the subject prior to completion of the “End of Study” eCRF. No additional data may be collected after a subject has been withdrawn from the study or withdraws his/her consent, for whatever reason. All open adverse events should be closed or documented as chronic. Data collected up to the point of subject withdrawal may be used. If such withdrawal is due to problems related to device safety or performance, the investigator shall ask for the subject’s permission to follow his/her status/condition.

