#### 9.1.1.3. Statistical Methods

For the primary safety endpoint, the Kaplan-Meier 12 month (365-day) primary safety event-free rate will be calculated. Subjects who withdraw from the study prior to 12 months without experiencing an event will be censored on the date of withdrawal. The 95% one-sided lower confidence limit of the observed safety event-free rate will be compared to the performance goal of 85%. If the lower confidence limit is greater than the performance goal, the null hypothesis will be rejected. The lower confidence limit will be calculated as the pointwise confidence limit using the log-log methodology.

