3.2.3 Statistical Methods

For the primary effectiveness endpoint, the Kaplan-Meier 12 month (365-day) primary effectiveness event-free rate will be calculated. Subjects who die or withdraw from the study prior to 12 months without experiencing an endpoint event will be censored on the date of death or the date of withdrawal. The 95% one-sided lower confidence limit of the observed primary effectiveness event-free rate will be compared to the performance goal of 50%. If the lower confidence limit is greater than the performance goal, the null hypothesis will be rejected. The lower confidence limit will be calculated as the pointwise confidence limit using the log-log methodology.

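### Protocol 7.2 and 8.14 let investigators withdraw already-ablated subjects and end their data collection, so the Kaplan-Meier rule can censor subjects for reasons linked to outcome, mainly for effectiveness

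*Protocol*

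**What the plan says.** **Reasons for withdrawal (Protocol 7.2).** "Reasons for withdrawal may include physician discretion, change in inclusion/exclusion status, subject choice to withdraw consent, lost to follow-up, or death". The list has no time limit. The section adds that withdrawal is discouraged and that its reason must be reported.

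**Data after withdrawal (same paragraph).** "No additional data may be collected after a subject has been withdrawn from the study or withdraws his/her consent, for whatever reason". Open adverse events are to be closed or recorded as chronic. Earlier data are kept: "Data collected up to the point of subject withdrawal may be used". The paragraph ends: "If such withdrawal is due to problems related to device safety or performance, the investigator shall ask for the" subject's agreement to continued follow-up. It does not say where such data would be recorded or whether they count toward an endpoint.

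**Repeat ablation (Protocol 8.14).** If the investigator prefers a non-study catheter for a repeat ablation, the subject may be withdrawn before that procedure. Pulmonary vein imaging is required first. Under 4.2 and 9.1.2, a repeat procedure for AF, or for new flutter or atrial tachycardia, on days 91 to 365 is a primary effectiveness event.

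**Censoring.** Protocol 9.1.1.3 (safety), with the same rule in 9.1.2.3 (effectiveness): "Subjects who withdraw from the study prior to 12 months without experiencing an event will be censored on the date of withdrawal". SAP 3.2.3: "Subjects who die or withdraw from the study prior to 12 months without experiencing an endpoint event will be censored". None of these rules looks at the reason for withdrawal.

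**Eligibility criteria that can change later (Protocol Table 4).** Exclusion 14: "Documented or suspected stenosis of any pulmonary veins". Exclusion 19: "Any electrocardiographically documented episode of Persistent AFib, defined as AFib lasting longer than 7 days from onset". Neither is tied to the date of enrollment.

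**The concern.** Kaplan-Meier censoring is valid only if subjects who leave have the same later risk as those who stay. Here an unblinded treating investigator may withdraw a subject for reasons that can follow from the treatment failing or causing harm. Follow-up then stops and the analysis treats the subject as a neutral loss.

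Both primary endpoints compare a lower confidence limit with a fixed performance goal, and there is no control arm in which the same bias might cancel. Removing likely failures from the risk set moves the estimate only upward, toward a pass. In a post-approval study meant to describe longer-term safety and effectiveness, the lost outcomes are also the ones of most interest.

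**Working it through.** **1. The plan's figures.** Inputs (Protocol 9.1.1.2, 9.1.2.2, 9.1.3.2): one-sided 5% level, 80% power, 7.5% attrition per year. The expected rates against the goals are 90% against 85%, 60% against 50%, and 65% against 50%. Take the smallest n from which exact binomial power stays at or above 80%, then divide by 1 − 0.075:
- Safety: 304/0.925 = 328.6, so 329.
- Primary effectiveness: 169/0.925 = 182.7, so 183.
- Secondary effectiveness: 76/0.925 = 82.2, so 83.

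All three stated sizes reproduce. The sample size is not at issue. Planned first-year attrition is 0.075 × 329 = 24.7, about 25 subjects.

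**2. Where an outcome can be lost.** Recorded events still count, so only withdrawal before a qualifying event matters.
- *Non-study repeat ablation, days 91 to 365.* Withdrawal under 8.14 comes before the procedure. If no qualifying recurrence is yet on file, the subject is censored.
- *Early persistent AF, for example on day 60.* Recurrence counts only from day 91. The subject now matches exclusion 19, and withdrawal means censoring before the evaluation period opens.
- *Suspected pulmonary vein stenosis, for example at month 5.* The subject matches exclusion 14, but the safety event needs symptoms and an intervention. Withdrawal before the intervention leaves it unrecorded.
- *Exclusions 8 and 9 (thrombus; CVA, TIA or PE).* Both are dated back from enrollment, so a post-ablation event cannot make them true.

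**3. Effectiveness, simulated.** N = 329, log-log lower limit against 50%, true rate exactly 50%, 7.5% non-informative attrition. Assumed, because the documents do not say: 10% of failures are acute and the rest are uniform over days 91 to 365. Non-acute failures: 329 × 0.5 × 0.9 = 148. The withdrawals below come on top of the planned attrition.

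| Non-acute failures withdrawn just before recording | Subjects (share × 148) | Mean KM estimate | False-pass rate |
|---|---|---|---|
| 0% | 0 | 50.0% | 4.5% |
| 5% | 7.4 | 51.6% | 13% |
| 10% | 14.8 | 53.4% | 30% |
| 20% | 29.6 | 56.8% | 73% |
| 25% | 37.0 | 58.7% | 90% |

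The last two rows need more withdrawals than the whole planned attrition of about 25, so the 5% and 10% rows are the more useful guide.

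**4. Safety, simulated.** True rate exactly 85%, against the 85% goal. Only effusion and fistula (to 3 months) and pulmonary vein stenosis (to 12 months) can be lost, since every other component counts only to day 7 or discharge. The false-pass rate is about 4.4% with nothing lost (90% of events acute).

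| Share of events that are acute (assumed) | 25% of later events lost | All later events lost |
|---|---|---|
| 95% | about 6% | 9% |
| 90% | about 6% | 17% |
| 80% | 10% | 45% |
| 70% | 12% | 76% |

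**5. SAP 5.6 tipping points.** Suppose 329 − 25 = 304 subjects complete at the planned rates, and the 25 withdrawals are turned into failures one by one (Clopper-Pearson, one-sided 95%).
- Safety: 274/304 event-free. With 8 failures, 291/329 has lower bound 0.851 (pass). With 9, 290/329 has 0.848 (fail).
- Effectiveness: 182/304 event-free. With all 25 as failures, 182/329 = 55.3% has lower bound 50.6% (pass).

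At the planned effectiveness rate the conclusion would therefore survive. The risk lies where the true rate is near the goal.

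**The case against.** The strongest reply is that the protocol means to keep these subjects.
- Eligibility is scheduled only at enrollment/baseline (Table 5), and up to 60 days may pass between consent and procedure. That gap is a natural setting for a change in eligibility.
- Follow-up visits collect imaging when stenosis is suspected. The event monitor is used in blanking to find early recurrences, and one repeat procedure in blanking is allowed.
- Withdrawal is discouraged, treated subjects are to be followed for three years, and 8.14 requires vein imaging before withdrawal.
- A subject with AF on day 60 is not yet a failure, and many non-study repeats will follow a recurrence that already counts.
- SAP 5.6.1 and 5.6.2 test the effect of withdrawals directly.

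All of this stands as evidence of intent, and it limits how often the problem should arise. It does not close the route: 7.2 sets no time limit, and 8.14 provides expressly for withdrawal after ablation. The tipping-point analyses show how fragile a result is, but success still rests on the censored Kaplan-Meier limit, and they cannot recover outcomes that were never collected.

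A reader might infer more than this, and the documents do not support it:
- *That failed or harmed subjects are to be withdrawn.* The text permits withdrawal and nowhere directs it.
- *That all later data are barred.* The closing sentence of 7.2 asks for continued follow-up after device-safety withdrawals. The fault is that the two sentences conflict.
- *That a post-ablation stroke or thrombus changes eligibility.* Exclusions 8 and 9 look back from enrollment.
- *That both event-free rates are biased upward as a matter of fact.* That depends on investigator behavior the documents do not describe.

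**Conclusion.** The concern holds as a gap in the rules. Together, 7.2, 8.14 and the censoring text allow a subject to leave the risk set because of how treatment is going, without the outcome being seen, and 7.2 contradicts itself on follow-up after device-safety withdrawals.

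Effectiveness carries most of the exposure. With a true rate at the 50% goal, losing about 7 non-acute failures (5%) roughly triples the false-pass rate, from 4.5% to 13%; losing about 15 (10%) takes it to 30%. Safety is much less sensitive unless a sizeable share of events falls after day 7 and most of those are lost.

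These figures rest on the assumed event timing, on the assumed share of outcome-related withdrawals, and on a true rate exactly at the goal. They describe what the plan leaves open and do not predict the trial's bias.

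**What to change.** 1. **Protocol 7.2, reasons.** Limit changed eligibility and physician discretion, as grounds for ending data collection, to subjects not yet ablated. Record a later condition that matches an exclusion criterion as an outcome or adverse event.
2. **Protocol 7.2, data after withdrawal.** Limit the no-data rule to withdrawal of consent for data collection. Reconcile it with the closing sentence on device safety and performance, and state that this follow-up enters the endpoint analysis.
3. **Protocol 8.14 and the censoring text (Protocol 9.1.2.3, SAP 3.2.3).** Keep subjects who have a non-study-catheter repeat in data collection, with their consent. In the analysis, count a decision to withdraw for such a repeat on days 91 to 365 as an effectiveness event and do not censor it.

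These changes affect data collection and analysis only, not catheter choice or other clinical management. N stays at 329 and no visits are added to the schedule. The cost is an amendment to two protocol sections and the matching censoring text, some added follow-up work, and possibly slightly lower event-free rates. The SAP 5.6 analyses should stay for the losses that remain.
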